3.2 Exclusion Criteria

- > 90 minutes/week of at least moderate intensity exercise over the previous three months as assessed by the Get Active Questionnaire (GAQ).
- Pregnancy
- BMI < 18 or > 45 kg/m²(16)
- Uncontrolled diabetes (changes in medication dosing over the previous three months or hemoglobin A1c $> 9\%$)(12)
- Active cardiac symptoms
- Severe medical comorbidities/psychiatric illness
- Decompensated cirrhosis (history of esophageal varices, ascites or hepatic encephalopathy)
- Cancer with life expectancy < 6 months
- MRI contraindications (severe claustrophobia, implanted ferrous metal)
- Other liver disease (positive hepatitis B surface antigen)
- Active weight-loss program participation or weight-loss supplement use
- Active substance abuse/smoking
- Inability to provide informed consent
- Institutionalized/prisoner
- Inability to walk > 2 blocks or $\frac{1}{4}$ mile
- Concurrent use of antiplatelet medications excluding aspirin 81 mg once daily as aspirin
- Non-English-speaking patients due to unavailability of translators for all visits/sessions

3.3 Early Withdrawal of Subjects

3.3.1 Criteria for removal from study

- Development of severe adverse event
- Subject consents to withdrawal
- Development of decompensated cirrhosis
- Failure to complete two successive weeks of exercise protocol.
 - Any subject who performs < 3 sessions in any given week during the 16-week study period will be required to extend their training by two additional weeks to

offset loss of physical conditioning. The power calculation accounts for expected study dropout (15-20% in exercise protocols).

3.3.2 Follow-up for withdrawn subjects

This will be an intention to treat analysis and subjects who are withdrawn will be followed at the same time points as who are enrolled still. E.g., they will receive a phone call at the completion point of the 16-week exercise program.

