1.2 Primary Study Endpoints

The primary outcome of interest is change in fibrinolysis as measured by PAI-1 level immediately following completion of the exercise and nutritional counseling program.

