Following their assessment and randomization, subjects will undergo baseline VO2 max testing at the Penn State Physical Medicine and Rehabilitation (PMR) Research Laboratories under the supervision of ACSM certified trained fitness professionals and study physicians. Anthropometric measurements will be completed at this assessment as well with dual-energy x-ray absorptiometry (DXA) body composition measurement, waist circumference, hip circumference and skin fold measurement. Following this, subjects will be given a Fitbit Charge2 with heart rate (HR) monitor along with an instruction form on how to use dietary log. Formal instruction on how to use the Fitbit Charge2 will be provided by trained study staff. This will include technical support with the Fitbit app that is supported on smartphones, the Fitbit website and Fitabase, a secure comprehensive data management platform for research studies, clinical trials and healthcare innovation projects utilized by >400 clinical trials since its inception. Participants will be instructed to record their food and beverage intake in a daily food diary through the Fitbit app and be provided information on how closely their daily food intake met the goals for macronutrients and energy.

Moderate intensity aerobic exercise: Subjects in the aerobic exercise group will be supervised to exercise 30 minutes, five times per week at a moderate intensity (HR target corresponding to 45-55% of their VO2max). Formal exercise instruction and supervision will be provided by ACSM certified fitness professionals at the Penn State University Fitness Center. Subjects will initiate their exercise program by walking on a treadmill for 15 minutes at their target HR goal and progressively increase the duration and frequency until the goal of 30 minutes of moderate intensity exercise five times a week is reached by the end of the four-week lead-in period. Subjects will then exercise five times a week under direct supervision in one of three locations; the Penn State University Fitness Center, the Cancer Center

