Exercise Medicine Unit or the Hershey Center for Applied Research. Aerobic exercise can be completed on either the treadmill, exercise bike, rowing machine or the elliptical machine. Subjects will be given the opportunity to complete these supervised sessions virtually or in-person as described above. If the subject chooses to complete the strength training sessions virtually, the study EP will schedule and complete exercise sessions using Penn State HIPAA complaint Zoom. Additional home exercise beyond the recommended sessions will be assessed by downloading data from the Fitbit Charge2. Review of downloaded information will take place once a week. Any subject who performs <3 sessions in any given week during the 16-week study period will be required to extend their training by two additional weeks to offset loss of physical conditioning. They can be extended no longer than 4 weeks. If subject misses more than 2 weeks of exercise sessions, they will be discontinued from the study.

Weekly review of dietary logs obtained via self-report through the FitBit application and secure web-based platform with directed feedback by trained study personnel (nutritionist) will also be provided either in-person, telephone interview or video chat. Additionally, participants will be given dietary education forms. In the event that the subject does not self-report their dietary intake through the FitBit platform, the 24-hour dietary recall data collection form will be utilized.

Study investigators will perform an interim history and physical examination on a monthly basis during the exercise protocol. If subject is required to extend protocol, interim history and physical examinations will continued to be performed on a monthly basis. The subject may complete these either in person or virtually.

The purpose of the post-exercise program liver biopsy is to observe changes in stage of fibrosis and NASH Activity Score. Liver biopsy is the gold standard to stage chronic liver disease from NASH and the benefit of disease staging and prognostication outweighs the small risk to the subject. Non-invasive methods of diseases staging (serologic scoring systems NFS, FIB-4) and ultrasound with elastography have inferior performance characteristics with much lower sensitivity and specificity and are hindered by significant inaccuracy with misclassification bias observed in upwards of 25%.(1, 93) Sub-

[REDACTED]

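### Intention to treat is promised, but the PAI-1 draw is not assured for exercise-arm subjects removed for missed sessions, and no missing-data method is named

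*Combined protocol and SAP*

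**What the plan says.** The primary outcome (section 1.2) is the change in "PAI-1 level immediately following completion of the exercise and nutritional counseling program". PAI-1 is a blood test. In the section 7.2 schedule, laboratories appear at Day 0 and again only in the end-of-programme column, nominally week 20.

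Section 3.3.1 lists as a criterion for removal "Failure to complete two successive weeks of exercise protocol". Section 7.2 words it differently: "If subject misses more than 2 weeks of exercise sessions, they will be discontinued from the study". Both refer to exercise sessions, which controls do not have.

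On what follows removal, section 3.3.2 first states that the analysis will be by intention to treat, then says that "subjects who are withdrawn will be followed at the same time points as who are enrolled still. E.g., they will receive a phone call", with the call placed at the end of the 16-week programme. Sections 8.3 and 10.7 repeat the intention-to-treat promise. Section 8.3 lists tests and unspecified multivariable regression, but no imputation, mixed model, sensitivity analysis or other rule for a missing PAI-1 value.

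Dropout is otherwise handled through sample size. Section 3.3.1 says "The power calculation accounts for expected study dropout (15-20% in exercise protocols". Section 8.2 expects 15-20% attrition, adds six subjects, and attaches 80.74% power to 28 exercise and 14 control subjects.

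**The concern.** An intention-to-treat analysis needs outcomes from everyone randomised, whatever their adherence. Here a removal trigger based on non-adherence acts in one arm, the outcome is measured once after baseline, and the one procedure named for removed subjects does not measure it. Staff who take the example as the whole rule would telephone and not draw blood, and that sample cannot be recovered later.

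The exercise arm would then be represented by its adherent members and the control arm by nearly everyone. The plan's own hypothesis is that exercise lowers PAI-1. If removed subjects benefit less, the difference among subjects with data overstates the intention-to-treat effect. Extra enrolment protects precision against lost observations; it does nothing about this selection.

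**Working it through.** **Inputs (section 8.2).** Difference 9 ng/mL; SD 14.0 exercise and 2.0 control; two-sided 0.05; unequal-variance t-test; 28 + 14 enrolled; attrition 15-20%; six extra subjects.

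**1. Reproduce the stated power.** SE = √(14²/n₁ + 2²/n₂), Satterthwaite df, noncentral t with noncentrality 9/SE.

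| Exercise + control | SE | df | Power |
|---|---|---|---|
| 22 + 11 | 3.045 | 22.7 | 80.74% |
| 24 + 12 (42 less six) | 2.915 | 24.8 | 84.3% |
| 28 + 14 | 2.699 | 29.1 | 89.7% |

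The stated figure is reproduced exactly at 22 + 11, that is 33 of 42 with 9 lost (9/42 = 21.4%). The six extra subjects would leave 36 (6/42 = 14.3% lost), which gives a different power. So the calculation appears to allow for missing outcomes, keeps the full 9 ng/mL effect, and is attached in the text to the wrong numbers.

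**2. Size of the possible bias.** Assume retained exercise subjects fall by 9, controls do not change, and a share f of the exercise arm is removed and keeps a share k of the benefit. The intention-to-treat difference is d = 9 × (1 − f + kf). Subjects with data still show 9, so the overstatement is 9/d − 1.

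| f | d, k = 0 | Overstatement, k = 0 | Overstatement, k = 0.5 | Overstatement, k = 1 |
|---|---|---|---|---|
| 5% | 8.55 | 5% | 3% | 0 |
| 10% | 8.10 | 11% | 5% | 0 |
| 15% | 7.65 | 18% | 8% | 0 |
| 20% | 7.20 | 25% | 11% | 0 |

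These shares are assumptions. The plan's 15-20% is study-wide, all-cause attrition: 0.15 × 42 = 6.3 and 0.20 × 42 = 8.4 subjects. If all of it fell in the exercise arm, f would be 6.3/28 = 22.5% to 8.4/28 = 30%, and with k = 0 the difference would be 6.98 to 6.30 (overstatement 29 to 43%).

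**3. Power if everyone is measured.** With k = 0 and n = 28 + 14, the exercise SD is √[(1 − f) × 14² + f × s² + f(1 − f) × 9²], where s is the SD of removed subjects.

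| f | Power, s = 14 | Power, s = 2 |
|---|---|---|
| 5% | 85.8% | 87.4% |
| 10% | 81.3% | 84.8% |
| 15% | 76.2% | 82.0% |
| 20% | 70.5% | 78.7% |

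Power crosses 80.74% at f of about 10.6% (s = 14) or about 17% (s = 2). These are best-case figures, since some recalled subjects will decline.

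**4. What imputation can do.** Imputing by arm alone, without auxiliary variables, has the completer difference of 9 as its expected value. Shifting imputed exercise-arm changes fully to no change gives 9 × (1 − f), the k = 0 column above. Shifting halfway gives 9 × (1 − f/2) = 8.78, 8.55, 8.33 and 8.10.

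**The case against.** The best defence is the text of section 3.3.2 itself. It is an affirmative rule, set beside the intention-to-treat promise; it keeps withdrawn subjects on the same follow-up timetable, ties contact to the end of the programme, and offers the telephone call only as an example. On that reading the draw is already included. This stands as a possible reading, but no section commits removed subjects to the draw, and the word discontinued in section 7.2 points the other way.

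A second defence is that the sample size covers dropout. It does so for precision, but not for selective loss in one arm. A third is that the bias is conditional, which is true: it is zero if removed subjects change like the rest.

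Some stronger readings are tempting and are not supported:

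- A reader might infer from the 22 + 11 match that a completers-only analysis is planned. Allowing for missing data in a sample size does not say how the data will be analysed.
- A reader might take 15-20% of the exercise arm as a ceiling, or as the expected removal rate. The documents support neither. Extension of training ("will be required to extend their training by two additional weeks") may limit removals, while concentration of attrition in one arm could push the share higher.
- A reader might see a contradiction between sixteen weeks and week 20. The progression in section 7.2, where the target of "five times a week is reached by the end of the four-week lead-in period", followed by sixteen weeks can give week 20. Sections 1.2 and 7.2 tie the draw to programme completion, and monthly examinations continue during an extension. What stays open is narrower: "They can be extended no longer than 4 weeks", and neither the schedule nor the 20-week duration in section 7.3 says when an extended subject's draw falls.

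**Conclusion.** The concern holds as a gap that should be fixed, not as proof of a biased analysis. The draw can be inferred for removed subjects but is not assured, the removal trigger is one-sided, and no missing-data method is named. The documents settle neither the direction nor the size of any bias. Under the assumption least favourable among those tabulated (no benefit in removed subjects), the overstatement is 5 to 25% for 5 to 20% removed, and 29 to 43% if all study-wide attrition fell in the exercise arm. With half the benefit kept it is 3 to 11% for 5 to 20% removed.

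The power misattribution is a separate point that does not depend on those assumptions: on the plan's own inputs, 80.74% does not describe 28 + 14. A reader might conclude that the trial is underpowered as designed; on its stated effect and SDs it is not. Power for the diluted intention-to-treat difference falls below the stated figure only beyond the crossings of about 10.6% or 17%, and those assume complete measurement.

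**What to change.** 1. **Sections 3.3.2 and 7.2.** State that removal for non-adherence, however that rule is finally worded, does not end outcome follow-up, and that every randomised subject who has not withdrawn consent is invited to the already scheduled end-of-study visit for the fasting PAI-1 draw.
2. **Section 8.3.** Analyse all available PAI-1 by randomised arm, name one missing-data method in advance, and add a sensitivity analysis that shifts imputed exercise-arm changes towards no change.
3. **Section 8.2.** Confirm the evaluable numbers behind 80.74% (22 + 11 reproduces it), reconcile them with the six extra subjects, and do not attach the figure to 28 + 14.
4. **Sponsor to reconcile.** The removal wordings in sections 3.3.1 and 7.2 differ, and the time of the end-visit draw for extended subjects needs stating. Both choices are the sponsor's; none is proposed here.

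The cost is mainly wording. The visit and assay are already in the schedule and the endpoint does not change. The downsides are the effort of recalling non-adherers, some of whom will decline, and a probably smaller estimated effect, with the power loss shown above if many are removed.

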4.0 Recruitment Methods

4.1 Identification of subjects

Potential subjects will be recruited from the surrounding area by a referral basis through both print marketing ("Dear Doctor" outreach letter) as well as in-person presentations by [name]. StudyKIK (<https://studykik.com>), an online recruitment service, will be utilized as well on a consultative basis in order to increase recruitment using a social media platform. The social media ad is submitted as an attachment to this protocol. Also, we will be using the Penn State Marketing Department to send targeted emails through the patient portal to patients that meet the basic study criteria. The email script is submitted as an attachment to this protocol.

Once potential subjects are referred to Penn State, they will be pre-screened by phone and/or in-person after their visit in hepatology clinic. Activity level will be assessed by the GAQ (attached). StudyFinder will be utilized.

The phone screen procedure is described in the supplemental attachment.

4.2 Recruitment process

StudyFinder, Penn State email blast through the patient portal and print materials will be utilized. StudyKIK will be used as a consultative service.

4.3 Recruitment materials

StudyFinder and print materials will be utilized. The print materials are recruitment letters to outside physician practices and also within Penn State as well as the email blast template letter. StudyKIK will develop IRB approved recruitment material in concert with Penn State and all IRB requirements.

4.4 Eligibility/screening of subjects N/A

5.0 Consent Process and Documentation

5.1 Consent Process

5.1.1 Obtaining Informed Consent

5.1.1.1 Timing and Location of Consent

Subjects will be invited for initial consultation performed by the study PI. Informed consent will take place at this consultation. Investigators must ensure that patients are clearly and fully informed about the purpose, potential risks, and other critical issues regarding clinical studies in which they volunteer to participate. Freely given written informed consent must be obtained from every subject prior to clinical study participation, including informed consent for any screening procedures conducted to establish subject eligibility for the study. The rights, safety, and well-being of the study patients are the most important

considerations and should prevail over interests of science and society. The consent process will occur in a private room in the Penn State Hershey Medical Center General Clinical Research Center (GCRC). The PI will carefully discuss the risks and benefits of study participation and review study procedures. The PI will make it clear that the subject's standard clinical care will not be affected in any way through participation or non-participation in the study. All questions will be answered prior to signing the informed consent document and the subject will verbalize understanding at the time of consent. The consent process will take approximately 15 minutes.

5.1.1.2 Coercion or Undue Influence during Consent

Investigators will explain the consent and allow for ample time to read and ask questions. Study procedures will be fully explained, voluntariness will be emphasized as well as the fact that no care will be denied regardless of the subject's decision.

5.1.2 Waiver or alteration of the informed consent requirement

Due to the extensive inclusion/exclusion criteria, patients will be asked to provide verbal consent to allow the study team to review their PHI to determine their eligibility for the study.

5.2 Consent Documentation

5.2.1 Written Documentation of Consent

Informed consent will be provided by a standardized process and informed consent form.

5.2.2 Waiver of Documentation of Consent (Implied consent, Verbal consent, etc.)

A waiver of consent documentation is requested for the phone screen. This is needed to allow for collection of PHI while screening potential subjects. Full and written consent will be recorded before any interventions begin.

5.3 Consent – Other Considerations

5.3.1 Non-English Speaking Subjects

Not planned at the time.

5.3.2 Cognitively Impaired Adults

5.3.2.1 Capability of Providing Consent

N/A

5.3.2.2 Adults Unable To Consent

N/A

5.3.2.3 Assent of Adults Unable to Consent

N/A

5.3.3 Subjects who are not yet adults (infants, children, teenagers)

5.3.3.1 Parental Permission

N/A

5.3.3.2 Assent of subjects who are not yet adults

N/A

6.0 HIPAA Research Authorization and/or Waiver or Alteration of Authorization

6.1 Authorization and/or Waiver or Alteration of Authorization for the Uses and Disclosures of PHI

Check all that apply:

- Not applicable, no identifiable protected health information (PHI) is accessed, used or disclosed in this study.** *[Mark all parts of sections 6.2 and 6.3 as not applicable]*
- Authorization will be obtained and documented as part of the consent process.** *[If this is the only box checked, mark sections 6.2 and 6.3 as not applicable]*
- Partial waiver is requested for recruitment purposes only (Check this box if patients' medical records will be accessed to determine eligibility before consent/authorization has been obtained).** *[Complete all parts of sections 6.2 and 6.3]*
- Full waiver is requested for entire research study (e.g., medical record review studies).** *[Complete all parts of sections 6.2 and 6.3]*
- Alteration is requested to waive requirement for written documentation of authorization (verbal authorization will be obtained).** *[Complete all parts of sections 6.2 and 6.3]*

6.2 Waiver or Alteration of Authorization for the Uses and Disclosures of PHI

6.2.1 Access, use or disclosure of PHI representing no more than a minimal risk to the privacy of the individual

6.2.1.1 Plan to protect PHI from improper use or disclosure

Information is included in the "Confidentiality, Privacy and Data Management" section of this protocol.

6.2.1.2 Plan to destroy identifiers or a justification for retaining identifiers

Identifiers will be destroyed per standard Penn State operating protocol after the required time frame has been met.

6.2.2 Explanation for why the research could not practicably be conducted without access to and use of PHI

This is a randomized, controlled trial.

6.2.3 Explanation for why the research could not practicably be conducted without the waiver or alteration of authorization

This is a randomized, controlled trial.

6.3 Waiver or alteration of authorization statements of agreement

Protected health information obtained as part of this research will not be reused or disclosed to any other person or entity, except as required by law, for authorized oversight of the research study, or for other permitted uses and disclosures according to federal regulations.

The research team will collect only information essential to the study and in accord with the 'Minimum Necessary' standard (information reasonably necessary to accomplish the objectives of the research) per federal regulations.

Access to the information will be limited, to the greatest extent possible, within the research team. All disclosures or releases of identifiable information granted under this waiver will be accounted for and documented.

7.0 Study Design and Procedures

7.1 Study Design

The aims of this research proposal are to better understand the potential for lifestyle interventions to reduce the elevated clot risk of patients with NASH without needing to take an anticoagulant (e.g. warfarin, low-molecular weight heparin). This proposal includes a RCT to determine the efficacy of supervised exercise on future clot risk. A RCT (n=42) of subjects with NASH will be conducted with a supervised 16-week moderate intensity aerobic exercise program as the intervention and the effect on fibrinolysis will be measured by change in PAI-1.

7.2 Study Procedures

Subjects will be invited for initial consultation performed by the study PI. This will be completed at the GCRC. If subjects are not currently in the Penn State system, they will be registered prior to this consultation through the Penn State Gastroenterology/Hepatology clinic staff ([name] or [name]). For all individuals who provide signed, informed consent, the following baseline measures will be completed:

- Comprehensive history and physical examination
- Anthropometric assessment [height, weight, BMI calculation]
- Physical activity questionnaire (IPAQ)
- Urine Pregnancy Test
- Nutrition counseling will be provided by a Registered Dietitian (RD) to promote a hypocaloric, low-fat dietary intake pattern. In the case that Dietitians are unavailable in person, counseling will be completed by phone or video chat using the Penn State Health-branded Zoom. Food Frequency Questionnaire (FFQ) will be used to assess their current dietary practices. Individual caloric needs will be calculated at baseline using the Mifflin St. Jeor equation, providing resting energy expenditure (REE), multiplied by the appropriate activity factor (AF) to yield total energy expenditure (TEE). Adjusted body weight (ABW) will be used when the participant's BMI is equal to or greater than 30. Five-hundred to 750 calories will be subtracted to promote an approximate weight loss of 1 pound per week for participants whose BMI classifies as overweight or obese. Macronutrient distribution will be recommended at 50-60% carbohydrate, 15-20% protein, and 20-30% fat with <10% total calories attributable to saturated fat. A sodium intake of <2,000 mg daily will be encouraged.

ABW & IBW Calculations:

- Use ABW to calculate REE when BMI ≥ 30
 - ABW calculation:
 - Males: $IBW + 0.38 \times (BW - IBW)$
 - Females: $IBW + 0.32 \times (BW - IBW)$
 - IBW calculation:
 - Males = $106 + 6 \times (Ht.(in)-60)$
 - Females = $100 + 5 \times (Ht.(in)-60)$

REE via Mifflin St. Jeor Equation:

- Male: $10(wt. (kg)) + 6.25(ht. (cm)) - 5(age (yr)) + 5 = REE \times AF = TEE$
- Female: $10(wt. (kg)) + 6.25(ht. (cm)) - 5(age (yr)) - 161 = REE \times AF = TEE$

| Activity Factors: | |
|--|--|
| Lifestyle and Physical Activity Level (PAL) | |

| | |
|--|---------------------|
| Seated work with no option of moving around and little or no strenuous leisure activity | 1.4-1.5 |
| Seated work with discretion and requirement to move around but little or no strenuous leisure activity | 1.6-1.7 |
| Standing work (e.g. housework, shop assistant) | 1.8-1.9 |
| Significant amounts of sport or strenuous leisure activity (30-60 min four to five times per week) | +0.3 (increment) |
| Strenuous work or highly active leisure | 2.0-2.4 |

Creatin
g a Caloric

Deficit for Weight Loss:

- Male and Female:
 - TEE - 500 kcals when BMI 25-29.9
 - TEE – 750 kcals when BMI 30-44.9
- Fasting laboratory testing (including baseline assessment of the hemostatic system). Subjects will be instructed to be fasting for at least nine hours. The following tests will be performed:
 - Complete blood count
 - Hemoglobin A1c
 - Thromboelastography
 - Insulin level
 - Basic metabolic panel
 - Hepatic panel
 - Lipid panel
 - Ferritin
 - ADAMTS13
 - Plasminogen activator inhibitor one
 - D-dimer
 - VonWillebrand Factor
 - Protein C
 - Protein S
 - Factor VII
 - Factor VIII
 - INR
 - Fibrinogen
 - Antithrombin
 - P-selectin
 - Adiponectin
 - Cytokeratin-18
- Calculation of non-invasive markers of fibrosis [NAFLD Fibrosis Score, Fibrosis-4 Index (FIB-4)
- Stool sample collection for 16S ribosomal microbiome assessment. A home stool collection kit and instructions will be provided to the subject. The kit will be labeled with the subject’s study code number.
- Additional genetic testing for single nucleotide polymorphisms (SNPs) of interest for exercise response, coagulation or NASH; subjects will not be notified of the results of these tests.
- Assessment of hepatic fat content with MRI-PDFF
- Baseline electrocardiogram (ECG) to be reviewed by study physicians
- HRQOL assessment via the PROMIS-CAT, an individual approach tailored to the health status of each subject offering significant improvements over the existing fixed length questionnaire evaluations of HRQOL (e.g. Short Form-36) that have been used almost exclusively in NASH (<http://www.nihpromis.org>). (51, 79-90) PROMIS includes gender- and age-matched normative data obtained from extensive testing of the U.S. population. PROMIS will be completed in-person under the direct supervision of trained study personnel.
- The liver biopsy obtained prior to enrollment will be reviewed by the pathology department to confirm the stage of fibrosis and NASH Activity Score.

Whole blood will be drawn in the Penn State Hershey GCRC (hours 730a-4p) by trained GCRC nursing or NASHFit research staff. Whole blood will be obtained and placed into the following tubes in the amounts described below [total nine teaspoons (tsp) of blood]:

- Three 3mL lavender (EDTA) top tubes (1.8 tsp)
- Two 4.5mL green (sodium heparin) top tubes (1.8 tsp)
- Three 6mL red top tube (3.6 tsp)
- Three 2.7mL blue (sodium citrate) top tubes (1.6 tsp)

Samples will then be delivered by NashFit study personnel to both the Clinical Laboratory for processing to serum and platelet poor plasma and also to [name] in the Institute for Personalized Medicine (IPM) for processing prior to transfer to the Endocrine Core Laboratory. Samples will be frozen and picked up from the Clinical Laboratories by IPM staff and brought to the IPM for storage and also the Genome Sciences and Bioinformatics Core for Taqman assay performance. Coded samples will be shipped through the IPM to [name], Associate Professor in University Park for metabolomics analysis. Results will be sent back to the IPM per standard IPM operating procedure. Stool samples will be obtained from the subject at home with a home collection kit and mailed directly from the subject to [name] (collaborator), Assistant Professor of Medicine, Juniata College. Stool samples will be processed, analyzed with 16S rRNA testing and stored in [name] laboratory.

Intervention Conditions: The aerobic exercise protocol is adapted from the landmark NASH-exercise trials by Sullivan *et al*(91) and Bacchi *et al*(92) that demonstrated the efficacy of exercise in improving intrahepatic fat and body composition but did not evaluate the effect on hemostasis and thrombosis risk. Once subjects have passed screening, they will be randomized 2:1 into either the exercise or control group respectively (two exercise subjects per one control subject) using a computer-generated randomized scheme in blocks of six by an independent statistician ([name] Public Health Sciences).

Following their assessment and randomization, subjects will undergo baseline VO2 max testing at the Penn State Physical Medicine and Rehabilitation (PMR) Research Laboratories under the supervision of ACSM certified trained fitness professionals and study physicians. Anthropometric measurements will be completed at this assessment as well with dual-energy x-ray absorptiometry (DXA) body composition measurement, waist circumference, hip circumference and skin fold measurement. Following this, subjects will be given a Fitbit Charge2 with heart rate (HR) monitor along with an instruction form on how to use dietary log. Formal instruction on how to use the Fitbit Charge2 will be provided by trained study staff. This will include technical support with the Fitbit app that is supported on smartphones, the Fitbit website and Fitabase, a secure comprehensive data management platform for research studies, clinical trials and healthcare innovation projects utilized by >400 clinical trials since its inception. Participants will be instructed to record their food and beverage intake in a daily food diary through the Fitbit app and be provided information on how closely their daily food intake met the goals for macronutrients and energy.

Moderate intensity aerobic exercise: Subjects in the aerobic exercise group will be supervised to exercise 30 minutes, five times per week at a moderate intensity (HR target corresponding to 45-55% of their VO2max). Formal exercise instruction and supervision will be provided by ACSM certified fitness professionals at the Penn State University Fitness Center. Subjects will initiate their exercise program by walking on a treadmill for 15 minutes at their target HR goal and progressively increase the duration and frequency until the goal of 30 minutes of moderate intensity exercise five times a week is reached by the end of the four-week lead-in period. Subjects will then exercise five times a week under direct supervision in one of three locations; the Penn State University Fitness Center, the Cancer Center

Exercise Medicine Unit or the Hershey Center for Applied Research. Aerobic exercise can be completed on either the treadmill, exercise bike, rowing machine or the elliptical machine. Subjects will be given the opportunity to complete these supervised sessions virtually or in-person as described above. If the subject chooses to complete the strength training sessions virtually, the study EP will schedule and complete exercise sessions using Penn State HIPAA complaint Zoom. Additional home exercise beyond the recommended sessions will be assessed by downloading data from the Fitbit Charge2. Review of downloaded information will take place once a week. Any subject who performs <3 sessions in any given week during the 16-week study period will be required to extend their training by two additional weeks to offset loss of physical conditioning. They can be extended no longer than 4 weeks. If subject misses more than 2 weeks of exercise sessions, they will be discontinued from the study.

Weekly review of dietary logs obtained via self-report through the FitBit application and secure web-based platform with directed feedback by trained study personnel (nutritionist) will also be provided either in-person, telephone interview or video chat. Additionally, participants will be given dietary education forms. In the event that the subject does not self-report their dietary intake through the FitBit platform, the 24-hour dietary recall data collection form will be utilized.

Study investigators will perform an interim history and physical examination on a monthly basis during the exercise protocol. If subject is required to extend protocol, interim history and physical examinations will continued to be performed on a monthly basis. The subject may complete these either in person or virtually.

The purpose of the post-exercise program liver biopsy is to observe changes in stage of fibrosis and NASH Activity Score. Liver biopsy is the gold standard to stage chronic liver disease from NASH and the benefit of disease staging and prognostication outweighs the small risk to the subject. Non-invasive methods of diseases staging (serologic scoring systems NFS, FIB-4) and ultrasound with elastography have inferior performance characteristics with much lower sensitivity and specificity and are hindered by significant inaccuracy with misclassification bias observed in upwards of 25%.(1, 93) Sub-

[REDACTED]
Control condition (standard of care). Subjects in the control condition will be instructed to continue their medical care at the discretion of their treating medical professional. They will be informed to maintain their current physical activity level. They will be given information from the American Liver Foundation to provide a basic understanding of NASH and to reinforce the counseling from their treating medical professional. We expect this information may result in a subject choosing to exercise, however, similar information-only interventions have led to only small effects, which are accounted for in the sample size calculation. Weekly phone calls will be performed by study personnel to ensure adherence to the protocol (no changes in activity). Subjects will report to Penn State on a monthly basis for anthropometric assessment in the GCRC to confirm their self-reports and study investigators will perform an interim history and physical examination at that time. Subjects may choose to complete this visit in person or virtually using Zoom. Subjects will also be given a Fitbit Charge2HR and downloaded data review will be performed monthly at study visits. These methods of compliance have previously been validated.(91)

This study will be a delayed treatment trial. Subjects randomized to the control condition will be given five months of fitness center membership to UFC and access to an ACSM certified fitness professional for training sessions following completion of the study protocol.

Penn State PM&R Research Laboratories: Housed at Hershey Center for Applied Research (HCAR), the 4,500 ft² facility is comprised of Exercise, Body Composition, Locomotor Training and Gait Laboratories

(Director-[name], collaborator). While the available exercise and body composition assessment equipment totals well over \$1,000,000 and includes multiple gait training devices, this study will utilize the following exercise equipment: Cosmed® K4B2 Portable Metabolic Device and ECG Telemetry system, ParvoMedics TrueMax® 2400 Metabolic Measurement System, and Quinton Q710 Stress Testing/Resting ECG System. Body composition resources include Lunar iDXA® DXA scanner, skinfold and anthropometric calipers.

Penn State University Fitness Center: Housed with the Penn State University Conference Center, the University Fitness Center has a plethora of resources including free weights and cardiovascular equipment necessary for this protocol. In addition, group fitness classes, gymnasium, locker room and shower facilities are available during convenient all-day hours, 7 days a week. In addition to the dedicated NASHFit exercise physiologist, there are an additional seven exercise physiologists on staff. There are private rooms available for study visits allowing for completion of assessment immediately before or after an exercise session by trained study personnel.

Follow-up. Subjects will be seen by a study investigator immediately after the completion of the 16-week exercise intervention. This will be completed at the Penn State Hershey GCRC and the PM&R research laboratory. A focused history and physical exam, anthropometric assessment including DXA scan, IPAQ, dietary log, cardiopulmonary fitness testing, laboratories, stool sample, MRI-PDFF, PROMIS and end of study survey will be completed. A sub-study of ten subjects will be required to complete a liver biopsy following sub-randomization at the completion of the exercise intervention. Samples collected for research purposes will be stored per standard SOP requirements of the Pathology Department. Subjects will be compensated (\$25 at baseline, \$25 at completion of the exercise regimen, \$100 following liver biopsy obtained at the completion of the exercise regimen if selected). They will also be allowed to keep their FitBit Charge2 HR. Finally, participants will receive a list of local fitness facilities available in the area. Twelve weeks after the end of the program, study staff will contact participants in the exercise arm by phone to complete a follow up questionnaire.

Paired liver biopsy samples (enrollment sample and post-exercise sub randomized sample) will be sent to a biotechnology company, Reveal Biosciences, to undergo an automated computerized ImageDx analysis to evaluate the severity of NASH. Samples will be shipped directly from the Pathology (where they are stored) and they will be de-identified.

Schedule of visits and study protocol assessments

| Visit | Initial Assessment | Exercise Instruction | Exercise Program or Control | End of exercise program |
|---|--------------------|----------------------|-----------------------------|-------------------------|
